6.1.4. Subgroup Analysis of Primary Efficacy Endpoint

No subgroup analyses will be performed.

6.2. Secondary Efficacy Endpoints

6.2.1. Definitions of Secondary Efficacy Endpoints

- The proportion of participants with HBsAg loss with and without anti-HBsAg seroconversion during the study
- The proportion of participants with HBeAg loss with and without anti-HBeAg seroconversion during the study in participants with CHB who are HBeAg positive at baseline
- The proportion of participants who remain off NUC treatment during FU
- The proportion of participants experiencing HBV virologic breakthrough (defined as confirmed HBV DNA ≥ LLOQ after 2 consecutive HBV DNA < LLOQ in participants who are complying with NUC therapy OR confirmed HBV DNA ≥ 1 log₁₀ IU/mL increase from nadir on treatment) during study treatment(s)

6.2.2. Analysis Methods for Secondary Efficacy Endpoints

The secondary efficacy analyses will be performed on FAS.

- The proportions of participants with HBsAg loss with and without anti-HBsAg seroconversion will be summarized by cohort and visit.
- The proportion of participants with HBeAg loss with and without anti-HBeAg seroconversion will be summarized by cohort and visit for participants who are HBeAg positive at baseline.
- The proportion of participants who remain off NUC treatment during FU will be summarized by cohort and FU visit.

Data collected on Visit Date CRF will be used to identify participants who entered FU phase. If a participant had any follow-up visit with nonmissing visit date, then this participant will be considered as entered FU phase.

For participants who entered the FU phase, if NUC treatment was ended no later than FU Week 1 visit, and there is no NUC treatment re-initiation during the FU phase, then this participant is considered as remaining off NUC treatment during FU phase. If partial start/stop dates are entered, any NUC treatment with the month and year (if day is missing) or year (if day and month are missing) of either start or stop date after FU Week 1 will be considered as using NUC treatments. Participants with completely missing NUC treatment start and stop dates will be considered as using NUC treatments, unless otherwise specified.

A list of NUC treatments can be found in Appendix 3.

• The proportion of participants experiencing HBV virologic breakthrough during study treatment(s) will be summarized by cohort.

The HBV virologic breakthrough is defined as confirmed HBV DNA ≥ LLOQ after 2 consecutive HBV DNA < LLOQ in participants who are complying with NUC therapy OR confirmed HBV DNA ≥ 1 log10 IU/mL increase from nadir during study treatments.

In addition, a summary table will be provided for HBsAg-related serology results. The proportion of participants who have ever had HBsAg loss, confirmed HBsAg loss, on-treatment HBsAg loss, posttreatment HBsAg loss (for participants with positive HBsAg at the end of the on-treatment period), HBsAg loss with HBsAb seroconversion, HBsAg loss with HBsAb seroconversion will be summarized.

For all the above summaries, within Cohort 2, the summary will be presented by treatment group (Group A or Group B) and HBsAg category (HBsAg > 3 and $\le 3 \log 10 \text{ IU/mL}$).

HBV serology definitions:

- **HBsAg loss**: HBsAg changing from positive at baseline to negative at any postbaseline visit.
- Confirmed HBsAg loss: HBsAg loss confirmed by any 2 consecutive results.
- HBsAg loss reversion: Any postbaseline HBsAg positive result following HBsAg loss.
- **HBsAb seroconversion**: HBsAb changing from negative or missing at baseline to positive at any postbaseline visit.
- Confirmed HBsAb seroconversion: HBsAb changing from negative or missing at baseline to positive at any postbaseline visit confirmed by any 2 consecutive results.
- **HBsAb** seroreversion: Any postbaseline HBsAb negative result following HBsAb seroconversion.

Both baseline and postbaseline borderline results for HBeAg, HBeAb, HBsAg, and HBsAb will be imputed as follows:

- HBsAb/HBeAb borderline/equivocal → HBsAb/HBeAb negative
- HBsAg/HBeAg borderline/equivocal → HBsAg/HBeAg positive

Missing data will be treated as a nonevent unless otherwise specified (eg, no HBsAg loss, no seroconversion, etc.)

HBeAg-related terminology is defined similarly.

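### HBeAg loss is a during-study secondary endpoint, but the visible plan summarizes HBeAg only by visit and does not state the during-study proportion

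*SAP*

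**What the plan says.** Section 6.2.1 of the SAP defines the endpoint: "The proportion of participants with HBeAg loss with and without anti-HBeAg seroconversion during the study in participants with CHB who are HBeAg positive at baseline". That is one proportion with the whole study as its time frame.

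Under the serology definitions in Section 6.2.2, HBsAg loss is "HBsAg changing from positive at baseline to negative at any postbaseline visit". The rule is then carried over: "HBeAg-related terminology is defined similarly". HBeAg loss is thus also an event that can occur at any postbaseline visit. The same definitions treat missing data as a nonevent unless otherwise specified.

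The HBeAg method in Section 6.2.2 is a by-visit summary: "anti-HBeAg seroconversion will be summarized by cohort and visit for participants who are HBeAg positive at baseline". HBsAg loss also gets a by-visit summary, but the section then adds: "In addition, a summary table will be provided for HBsAg-related serology results". The contents of that table begin: "The proportion of participants who have ever had HBsAg loss, confirmed HBsAg loss, on-treatment HBsAg loss, posttreatment HBsAg loss". No matching table is stated for HBeAg.

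**The concern.** The endpoint asks how many baseline HBeAg-positive participants lost HBeAg at some time in the study. The planned output shows how many were HBeAg negative at each visit. A set of visit rows does not show whether the participants negative at one visit are the same ones negative at another, so a reader cannot recover the first quantity from the second.

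A named secondary endpoint could then be reported through a quantity that does not match its definition. If the plan stays silent, the choice between a cumulative figure and one of the visit rows could be made after the results are known.

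**Working it through.** **What is there to reproduce.** The visible SAP gives no rate, sample size or precision figure for this endpoint. The check compares definition with method and then asks when the two quantities differ.

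**Definition against method.**
- HBsAg loss: during-study endpoint (6.2.1). Output is by cohort and visit, plus a table of participants who ever had a loss (6.2.2).
- HBeAg loss: during-study endpoint (6.2.1). Output is by cohort and visit only (6.2.2).
- Virologic breakthrough: during-treatment endpoint (6.2.1). Output is by cohort, with no mention of visit (6.2.2).

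Of these three, only HBeAg loss lacks an output on the time scale of its definition.

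**Direction of the difference.** Let N(i,v) = 1 if participant i has a negative HBeAg result at visit v, and 0 if the result is positive or missing. Then ever(i) = max over v of N(i,v), so N(i,v) ≤ ever(i) at every visit. Counting missing as a nonevent keeps the denominator n fixed. Averaging gives

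(1/n) Σ N(i,v) ≤ (1/n) Σ ever(i).

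Equality holds at the last visit when every participant who lost HBeAg is still negative and observed there.

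**Size of the subset.** Section 1.2 sets a minimum of 20% HBeAg positive per cohort: 0.20 × 40 = 8 in Cohort 1 and 0.20 × 60 = 12 in Cohort 2. If the 12 split 2:1, that is about 8 in Group A and 4 in Group B. The split is an assumption, because randomization is stratified by HBsAg and not by HBeAg.

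**Extreme illustration (assumed outcomes).** Take n = 8, with three participants each negative at one visit only, all at different visits.
- During the study: 3/8 = 37.5% (exact 95% interval 8.5% to 75.5%).
- Any single visit: at most 1/8 = 12.5% (exact 95% interval 0.3% to 52.7%).

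The intervals are added for scale; Section 6.2.2 plans none for this endpoint.

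**Less extreme patterns (assumed rates).** The simulation used 8 participants and 5,000 runs per pattern. It had 15 postbaseline HBeAg visits, from the Cohort 1 schedule in Appendix Table 1: 10 on treatment (Weeks 4 to 36) and 5 in follow-up (Weeks 4, 12, 24, 36 and 48). The visit of first loss was equally likely to be any of the 15. Reversion was a constant chance per visit, and missingness was independent by visit.

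| Assumed pattern | Ever | Highest visit (mean) | Last visit |
|---|---|---|---|
| 40% lose, sustained, none missing | 39.9% | 39.9% | 39.9% |
| 40% lose, sustained, 10% missing | 39.5% | 38.6% | 35.8% |
| 40% lose, 10% revert per visit, none missing | 39.9% | 29.8% | 21.2% |
| 40% lose, 30% revert per visit, none missing | 40.2% | 22.5% | 8.7% |
| 40% lose, each at one visit only, none missing | 39.4% | 15.5% | 2.6% |
| 20% lose, 30% revert per visit, none missing | 19.9% | 13.7% | 4.4% |

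Missing results alone cost little at the highest visit (39.5 − 38.6 = 0.9 points) and more at the last visit (39.5 − 35.8 = 3.7 points). Reversion drives the large gaps: at 10% per visit, 39.9 − 29.8 = 10.1 points at the highest visit and 39.9 − 21.2 = 18.7 points at the last.

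**The case against.** The strongest reply is that by-visit reporting may be the intended analysis. The HBsAg endpoint has the same during-study wording and the same by-visit method, and its table of ever-losses is introduced as an addition. On that view, during the study names only the period over which visits are tabulated. A cumulative reading of the by-visit summary is also possible. Neither reading is stated. The any-visit definition of loss and the by-cohort summary of breakthrough both point the other way. The event itself is defined for HBeAg, so what is absent is its summary.

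Three stronger readings are tempting, and the document does not support them:
- A reader might infer that by-visit rows understate the endpoint whenever losses begin at different visits. They do not: three losses that begin at different visits and persist all appear at the last visit.
- A reader might infer that 37.5% against 12.5% is the expected gap. It needs each loss to revert, or to go unobserved, before the next one appears, and nothing in the SAP predicts that. Section 3.8.3 also selects the most favorable HBeAg result within a visit window, so a repeat positive in the same window does not hide a loss.
- A reader might infer that the trial will never compute this proportion. The contents list shows a redacted entry after 6.2.2 and a Section 6.4 on other efficacy analysis whose text is not shown. The gap can be confirmed only for the visible plan, although Section 6.2.2, where secondary methods belong, is visible.

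It is also fair to say that the stakes are small. Section 3.5 rules out formal testing, and the subset is about 8 participants in Cohort 1 and 12 in Cohort 2 at the planned minimum.

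**Conclusion.** The point holds as a mismatch between a secondary endpoint and its stated method. Followed as written, the visible Section 6.2.2 does not yield the during-study HBeAg proportion, and the by-visit rows cannot rebuild it.

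Whether reported figures would be too low depends on the data. The gap is zero if all losses are sustained and observed. It was about 1 point at the highest visit under the assumed 10% missingness without reversion, and 10 points or more under the assumed reversion rates with 40% losing HBeAg. The 25-point gap (37.5% − 12.5%) belongs to an assumed extreme. The loss, reversion and missingness rates are all assumptions, because the SAP gives none. This is a minor correction with no effect on the primary analysis.

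**What to change.** In Section 6.2.2, add the proportion of participants with HBeAg loss at any postbaseline visit, with and without HBeAb seroconversion, among those HBeAg positive at baseline. Present it by cohort and by group within Cohort 2. State that this is the estimate of the secondary endpoint in Section 6.2.1, and keep the by-visit table alongside it. Confirmed, on-treatment and posttreatment HBeAg loss are not part of the endpoint and need not be added to close the gap.

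The cost is one sentence in the SAP and one additional summary from HBeAg and HBeAb results already collected. If the SAP is already final, Section 1 provides for documenting the change in the clinical study report.

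### The off-NUC rule counts a participant who stopped NUC and was lost early in follow-up as a success through FU Week 48, and it defines no status at each visit for the by-visit summary

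*SAP*

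**What the plan says.** SAP Section 6.2.1 names the secondary endpoint: "The proportion of participants who remain off NUC treatment during FU". Section 6.2.2 sets its analysis as follows.

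- Analysis set: "The secondary efficacy analyses will be performed on FAS".
- Display: "The proportion of participants who remain off NUC treatment during FU will be summarized by cohort and FU visit".
- Entry to follow-up: "If a participant had any follow-up visit with nonmissing visit date, then this participant will be considered as entered FU phase".
- Success, for those who entered: the first condition is that NUC had stopped by FU Week 1; the second, with its consequence, reads: "there is no NUC treatment re-initiation during the FU phase, then this participant is considered as remaining off NUC treatment during FU phase".
- Undated NUC records: "Participants with completely missing NUC treatment start and stop dates will be considered as using NUC treatments, unless otherwise specified". Partial dates falling after FU Week 1 are likewise read as NUC use.
- At the end of the section, among the HBV serology definitions: "Missing data will be treated as a nonevent unless otherwise specified". The examples given are HBsAg loss and seroconversion.

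Table 3-10 runs the follow-up windows to FU Week 48 (FU Day 337).

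**The concern.** Success is the absence of a recorded restart, and one follow-up visit is enough to qualify. A participant who ended NUC by FU Week 1, attended once and then left cannot have a later restart recorded. The rule still credits that participant with the whole phase. The safeguards for missing and partial dates act on NUC records that exist. They do not reach a person who left before any restart could be recorded.

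There is a second gap. The table must be laid out by FU visit, but the only status defined is one yes/no for the whole phase. No visit denominator is given: it could be the FAS, those who entered FU, or those seen at the visit. Two programmers could follow the text and produce different tables.

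There is a third gap in wording. Cohort 2 is viremic, and its participants receive TAF only if they meet criteria to start it (Section 1.2, Figure 1-1, note a). A condition that NUC was ended does not describe someone who never took it.

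At stake is a named secondary endpoint in a descriptive study, where the estimate is the whole result. At the planned sizes one participant is 1/40 = 2.5 points in Cohort 1 or Cohort 2 Group A, and 1/20 = 5 points in Group B.

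**Working it through.** The SAP states no off-NUC rate, restart rate or follow-up loss for this endpoint, so there is no figure to reproduce. What follows is illustrative.

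**Assumptions.** Everyone in the denominator entered FU and was off NUC at FU Week 1. A fraction L is lost soon afterwards with no restart recorded. The true risk of restarting by FU Week 48 is r, the same in lost and retained participants. Ranges: L = 5–20% (2 to 8 of 40, or 1 to 4 of 20) and r = 20–60%.

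**Whole-phase proportion**

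- SAP rule: (1 − L)(1 − r) + L
- Truth: 1 − r
- Lost counted as not off NUC: (1 − L)(1 − r)
- SAP rule minus truth: L × r
- SAP rule minus lost-as-not-off: L

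| L | r | SAP rule | Truth | Lost = not off NUC | Excess over truth |
|---|---|---|---|---|---|
| 5% | 20% | 81% | 80% | 76% | 1 point |
| 10% | 20% | 82% | 80% | 72% | 2 points |
| 10% | 40% | 64% | 60% | 54% | 4 points |
| 20% | 40% | 68% | 60% | 48% | 8 points |
| 20% | 60% | 52% | 40% | 32% | 12 points |

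If the lost restart at a different risk r′, the truth is (1 − L)(1 − r) + L(1 − r′) and the excess is L × r′. It reaches its ceiling of L only if all of the lost restarted. If only a fraction f of the denominator was off NUC at FU Week 1, with the same loss, the excess is f × L × r. For example, f = 50% (assumed) with L = 10% and r = 40% gives 0.5 × 0.1 × 0.4 = 2 points.

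**By visit.** Take L = 10%, r = 40% at FU Week 48 and a constant restart hazard, so the true proportion at week w is 0.6^(w/48). The second column repeats the whole-phase status at every visit. The last applies a visit-level status that counts the lost as not off NUC, 0.9 × truth.

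| FU week | Whole-phase status repeated | Truth | Difference | Visit-level, lost = not off NUC |
|---|---|---|---|---|
| 4 | 64.0% | 95.8% | −31.8 | 86.2% |
| 12 | 64.0% | 88.0% | −24.0 | 79.2% |
| 24 | 64.0% | 77.5% | −13.5 | 69.7% |
| 36 | 64.0% | 68.2% | −4.2 | 61.4% |
| 48 | 64.0% | 60.0% | +4.0 | 54.0% |

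Repeating the whole-phase status makes late restarters failures from the start, so it understates the earlier visits. In this example the result is too high only at the last visit.

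**Never-treated participants.** The success condition needs NUC to have ended. A participant with no NUC record has no end date. Read literally, the sentence on completely missing start and stop dates could class that person as a NUC user, which would push Cohort 2 downward.

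**The case against.** The strongest defence is the missing-data sentence at the end of Section 6.2.2. If it covers this endpoint, and the event is staying off NUC, then lost participants already count as not off NUC and the upward bias disappears. That reading is possible but not secured. The sentence stands among the serology definitions, has serology examples and gives way where something else is specified. It also does not say whether the event is staying off or restarting; if restarting is the event, it produces the problem. For the same reason a reader should not infer that the rule overturns a missing-data principle set for this endpoint. None is clearly set.

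Three other stronger readings are tempting and not supported.

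- *Each early dropout is 2.5 points of error in Cohort 1, so four of 40 make 10 points.* That gap is against counting every dropout as a failure, not against the truth. If 32 of 36 retained participants stay off NUC (88.9%) and the four lost behave alike, the rule gives 36/40 = 90%, an excess of about 1 point. Nor does every dropout add to the count. Section 1.2.1 no longer requires NUC cessation in Cohort 1 and Section 3.8.2 allows TAF to continue, so someone still on NUC after FU Week 1 fails the rule anyway.
- *The rule inflates every visit.* Repeating the whole-phase status would lower the earlier visits.
- *The whole-phase status will be copied to each visit.* The SAP does not say so. Status up to each visit is an equally open reading; the fault is that neither is fixed.

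A link between dropout and restarting is plausible, but the SAP has no data on it. The objection that the never-treated wording is a quibble has some force, since the intent is easy to guess, but one sentence settles it. It is also true that no formal testing is planned (Sections 3.5 and 6.1.2), that premature FU discontinuation is tabulated (Section 4.1), and that undated NUC records are handled conservatively.

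**Conclusion.** The concern stands, limited in size and direction. As written, the rule counts participants who ended NUC by FU Week 1 and were then lost as off NUC for the whole phase, so the whole-phase and late-visit proportions lean upward. Under equal restart risk in lost and retained participants, with all off NUC at FU Week 1, the excess is 4 points at 10% loss and 40% restart, and 1 to 12 points over the ranges shown. It is larger if the lost restart more often, and smaller if they restart less often or if fewer participants had stopped NUC. None of these rates comes from the SAP.

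Separately, and without any assumption, the required by-visit summary has no visit-level status or denominator, and the success condition does not literally cover Cohort 2 participants who never took NUC. No test or error rate is affected. The case is for a correction before the table is produced.

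**What to change.** Revise Section 6.2.2 as follows.

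1. Define status cumulatively at each FU visit: off NUC means no NUC use after FU Week 1 up to that visit's date, with follow-up evidence at or after that visit.
2. Fix one denominator for all visits, either the FAS or participants who entered FU, and state it.
3. Count a participant whose last contact precedes the visit as not off NUC. Count a missed visit followed by a later visit with no NUC record as off NUC. The schedules in Appendix 1 collect concomitant medications at every FU visit, so the later visit supplies the evidence; scoring each missed visit as a failure would misclassify these participants.
4. State that participants with no NUC record count as off NUC, subject to the same follow-up evidence, and that the missing-date sentence applies only to NUC records that exist without dates.
5. Report a Kaplan-Meier estimate of time to NUC re-initiation, censored at last contact, among participants off NUC at FU Week 1.
6. At the Primary Analysis, stop the display at FU Week 24, because later visits are not yet due for participants still in follow-up.

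The cost is SAP wording, one derivation and one added estimate. Section 1 provides that changes after finalization are documented in the CSR. The proportion that counts lost participants as not off NUC is conservative (54% against a true 60% in the worked example), so it should be read beside the Kaplan-Meier estimate, which in turn assumes that censoring is unrelated to restarting.

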7. SAFETY ANALYSES

7.1. Adverse Events and Deaths

7.1.1. Adverse Event Dictionary

Adverse events (AEs) will be coded using the current version of the MedDRA. System organ class (SOC), high-level group term (HLGT), high-level term (HLT), preferred term (PT), and lower-level term (LLT) will be provided in the AE dataset.

7.1.2. Adverse Event Severity

Adverse events are graded by the investigator as Grade 1, 2, 3, or 4 according to toxicity criteria specified by Gilead Grading Scale for Severity of Adverse Events and Laboratory Abnormalities Version 01 April 2015, with the exception of infusion-related reactions (IRRs). For grading of IRRs, the Common Terminology Criteria for Adverse Events (CTCAE) Version 5.0 are used.

The severity grade of events for which the investigator did not record severity will be categorized as "missing" for tabular summaries and data listings. The missing category will be listed last in summary presentation.

7.1.3. Relationship of Adverse Events to Study Drug

Related AEs are those for which the investigator selected "Related" in the eCRF in response to the question for the relatedness to each study treatment, ie, SLGN, TAF, nivolumab, or VIR-2218.

Relatedness will always default to the investigator's choice, not that of the medical monitor. Events for which the investigator did not record relationship to study drug will be considered related to study drug for summary purposes. However, by-participant data listings will show the relationship as missing.

7.1.4. Relationship of Adverse Events to Study Procedures

Study procedure related AEs are those for which the investigator selected "Yes" on the AE case report form (CRF) to the question of "Related to Study Procedures." Relatedness will always default to the investigator's choice, not that of the medical monitor. Events for which the investigator did not record relationships to study procedure will be considered related to study procedure for summary purposes. However, by-participant data listings will show the relationship as missing.

